The DPR group will be placed in a silo within 2 hours of admission to the NICU with a drain placed at the top of the silo as described below. At the time of silo placement for staged procedure, the JP drain will be placed intra-abdominally beneath the fascia at the base of the small bowel mesentery. Subjects will be treated with adjuvant direct peritoneal resuscitation (DPR) until the abdomen is closed, which is usually four to five days. No additional incisions will be made.

Set-up of Silo

The silo will be placed within 2 hours of admission to the NICU as per standard of care. Through the top of the silo a flat 10 mm JP drain will be placed and secured with suture and sterile, adhesive tape at the top of the silo to create a seal. This drain will allow for aspiration of peritoneal fluid for specimen collection and instillation of Dianeal 1.5% (DPR group only).

Drain manipulation

The JP drain will be steriley placed through top of the silo at time of the silo placement into abdominal cavity. A closed system will be created using Medline One-link Needle-free IV connector to the drain to allow for sterile placement of the dialysate. There will not be any planned drain replacements. If the drain or silo replacement is necessary due to unforeseen circumstances, the abdomen will be prepped in standard sterile fashion and the silo with drain will be replaced in same manner as when it was initially placed. There will be no increased risk of underlying infection with placement of the silo or drain.

Set-up for DPR

The dialysate fluid will be placed in syringe under sterile conditions in the Research Pharmacy. The syringe will then be connected to the JP drain via a needle free IV connector. The connector will be cleaned with an alcohol wipe at the time of fluid instillation into the JP drain.

1. Instillation of fluid - Process will be repeated every 6 hours (\pm 30 minutes) until abdomen is closed.
 - a. Fluid will be warmed at bedside using dry heat not to exceed 37°C/98°F.
 - b. An initial bolus of 10 mL/kg of Dianeal 1.5% via the JP drain will be given. If tolerated, each subsequent bolus will be increased by 10 mL/kg of Dianeal 1.5% up to a goal infusion of 40 mL/kg of Dianeal 1.5% (to a maximum volume of 100 mL) as tolerated via the JP drain.
 - c. The maximum dose that will be administered, based on a historical data (CHND), is 100 mL.

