- b. X-ray reads daily by radiology
- c. Reason and time of change in feeding regimen
- d. Stool output

15. Adverse events*

- a. The durability of treatment effectiveness as well as potential longer-term adverse events will be assessed via chart reviews of pediatric follow-up visits or follow-up phone calls up to 90 days after discharge.

Timeline

We estimate that after approval, it will take approximately 2-3 years to accrue and follow subjects as a single-site study and 6 months to analyze data and prepare manuscripts.

Calendar of Procedures and Assessments

Assessment	Screening (Day of Birth 0-12 hrs)	Staged Reduction (Day of Birth 0-24 hrs)	Day of Life 1-7	Day of Closure	Post-Closure Day 1	Post-Closure Day 2 until Discharge	Day of Discharge	Post-Discharge Follow-Up (up to 90 days)
Informed Consent	X							
Randomization	X							
Silo/JP Drain placement ¹	X							
Verify lab values for eligibility		X						
Vitals (HR, RR, BP/MAP, SpO2)	X ²	X ²	X ²	X ²	X ³	X ³	X ⁴	
Weight	X	X	X	X	X	X	X	
Routine Labs ⁵	X			X	X	X	X	
Research Labs ^{6,7}	X	X	X	X	X	X	X	
G-tube placement ⁴	X ³							
Instill DPR ⁸	X		X					
Intake/Output		X ²	X ²	X ²	X ³	X ⁴		
Glucose pre- & post-infusion ⁹	X	X	X					
Bedside ultrasound				X		X ¹⁰		
AE assessment ¹¹	X		X	X	X	X	X	
Remove OG-tube & Initiate EBM/Formula ¹						X		
Chart Review or Phone Call							X	

¹ Silo placement only or silo and JP drain placement per randomized group assignment

² Q6 hrs (± 30 min) for 48 hrs after maximum volume, then Q12 hrs (± 30 min)

³ Q12 hrs (± 30 min)

⁴ Per NICU Standard Practice

⁵ All: CBC w/ Diff, Magnesium, Sodium, Potassium, Chloride, Bicarbonate/CO₂, BUN, Creatinine, Calcium, Phosphate, Albumin, Glucose, Q24 hrs (± 30 min)

⁶ SoC Group: Lactate only, Q24 hrs (± 30 min) same time as Routine Lab

⁷ DPR Group: Lactate, Sodium, Potassium, Glucose, Q6 hrs (± 30 min) for 24 hrs after maximum volume, then Q12 hrs (± 30 min)

⁸ DPR Group: Q6 hrs (± 30 min), dwell for 1 hr, then remove excess fluid - 10 mL/kg initial bolus, then increase by 10 mL/kg up to 40 mL/kg (100 mL maximum volume)

⁹ DPR Group only: Glucose within 1 hr prior to every infusion and 1 hr (± 15 min) every post-infusion for the first day (24hrs) of treatment

¹⁰ Daily bedside ultrasound will be performed from post-closure Day 1 to time of full feeds and if feeds are stopped for any reason

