- Hospital Discharge
- Adverse events

Post-Discharge Follow-up (up to 90 days following hospital discharge)

- Chart review or phone call
- Adverse events

Risks and Benefits

Both groups will have the same underlying risks secondary to gastroschisis repair, anesthesia and surgery independent of the silo placement. These risks include allergic reaction to medicines, breathing problems (including problems requiring intubation and ventilation), bleeding, infection, inflammation of peritoneum, organ injury, problems with digestion and malabsorption, dysmotility, and abdominal wall hernia.

As this is a novel procedure, the risk for infection secondary to placement and retention of the JP drain, for the DPR group, is unknown. However, given that the JP drain will be steriley placed and secured to the silo bag under sterile conditions, we estimate that the risk of JP drain placement and retention in the silo would not be appreciably higher than the risk of infection secondary to standard gastroschisis repair (12.5%). Additionally we estimate that the risk for infection secondary to placement and retention of JP drain within the peritoneum beneath the fascia at the base of the small bowel mesentery would not be substantially higher than the risk of infection secondary to standard gastroschisis repair (12.5%).

Subjects may also have the risk of potential for loss of confidentiality. Measures to protect the confidentiality of study participants will be implemented as described in the Data Handling and Recordkeeping section below.

Additional risks for babies who undergo DPR treatment may include electrolyte imbalances, which will be monitored via laboratory values.

Title: Direct Peritoneal Resuscitation in Gastroschisis

PI: [name]

Sponsor: UAMS

Babies in the DPR group are at risk for Encapsulating Peritoneal Sclerosis, allergic reaction to corn (including anaphylaxis), and possible reactions with insulin or other concomitant medications and treatments.

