5. Infections [21]

Definitions

Adverse Event

An adverse event (AE) is any symptom, sign, illness or experience that develops or worsens in severity during the course of the study. Intercurrent illnesses or injuries should be regarded as AEs. Abnormal results of diagnostic procedures are considered to be AEs if the abnormality:

- results in study withdrawal
- is associated with a serious AE
- is associated with clinical signs or symptoms
- leads to additional treatment or to further diagnostic tests
- is considered by the investigator to be of clinical significance

Serious Adverse Event

Serious AE (SAE) means any untoward medical occurrence at any dose: An event is “serious” if it involves considerable detriment or harm to one or more persons (who may or may not be participants), or required intervention to prevent one or more persons from experiencing considerable detriment or harm. SAEs include:

- Death
- Life-threatening experience – Disease or condition where the likelihood of death is high unless the course of the disease/condition is interrupted or diseases/conditions with potentially fatal outcomes where the endpoint of the clinical trial analysis is survival
- Inpatient hospitalization or prolongation of hospitalization
- Persistent or significant disability/incapacity
- Congenital anomaly/birth defect in participant's offspring

Title: Direct Peritoneal Resuscitation in Gastroscisis

PI: [name]

Sponsor: UAMS

- Any other important medical event that, based upon appropriate medical judgment, may jeopardize the participant and may require medical or surgical intervention to prevent one of the outcomes listed above. Examples include allergic bronchospasm requiring intensive treatment in an emergency room or at home, blood dyscrasias or convulsions that do not result in inpatient hospitalization, the development of drug dependency or drug abuse, suicidal ideation or attempts, or the unintentional revealing of some genetic information to insurers.

Related

An event is “related” if more likely than not it was caused by the research activity.

Unexpected

An event is “unexpected” when its specificity, nature, severity or incidence is not accurately reflected in the consent form, protocol, or investigator’s brochure previously reviewed and approved by the IRB. Examples include a lower rate of response to treatment or a side effect that is more severe than initially expected.

Study Period

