1. Seriousness (grading of event)
2. Relatedness to study treatment
3. Expectedness

Steps to Determine if the Event Requires Expedited Reporting:

1. Determine whether the adverse event is related to the investigational drug. Attribution categories are as follows:
 - Unrelated
 - Unlikely
 - Possible
 - Probable
 - Definite
2. Determine expectedness of event. Expected events are those previously identified resulting from administration of the agent. An adverse event is considered unexpected when the type or severity of the event is not listed in the package insert, protocol, or consent form.

Note: This includes all events that occur within 30 days of the last dose/use of protocol treatment. Any event occurring more than 30 days after the last dose that is possible, probably, or definitely attributable to the investigational drug must be reported according to the instructions above.

Expedited Reporting of AEs

Institutional Review Board Reporting

Only adverse events meeting the UPIRTSO (Unanticipated Problem Involving Risks to Subjects or Others) will need to be reported to the UAMS IRB within the required 10-day allotment of being notified of the event. UPIRTSO requires that an unanticipated problem meet the following qualifications: a) unanticipated or unexpected; b) related to the research; and c) involves new or increased risk to the subject(s). All other adverse events should be recorded and reported to the UAMS IRB at continuing review.

Sponsor Reporting

The Sponsor will be promptly notified of all SAEs that are related to the study intervention and unanticipated/unexpected. These SAEs will be reported to the Sponsor using the FDA MedWatch 3500A. All other SAEs will be reported to the Sponsor and FDA in the Annual Progress Report. The Sponsor will report events to FDA in accordance with 21 CFR 312.

Deaths that are related to research will be reported to the Sponsor immediately upon Investigator notification. A death due to a terminal condition of the research participant would be considered anticipated and not related to the research. THE SPONSOR WILL REPORT DEATHS TO FDA IN ACCORDANCE WITH 21 CFR 312.

Title: Direct Peritoneal Resuscitation in Gastroschisis

PI: [name]

Sponsor: UAMS

Monitoring

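### The attribution steps ask only about the investigational drug, which is narrower than the protocol's definition of related and its reporting criteria, so harm from the drain or research blood draws can be miscoded and reported late

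*Combined protocol and SAP*

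**What the plan says.** The section Steps to Determine if the Event Requires Expedited Reporting opens with "Determine whether the adverse event is related to the investigational drug", followed by five categories from Unrelated to Definite. No other attribution scale appears in the document. Step 2 turns to expectedness and starts: "Expected events are those previously identified resulting from administration of the agent". Its next sentence widens the test by pointing to the package insert, protocol and consent form. The closing note on late events says: "Any event occurring more than 30 days after the last dose that is possible, probably, or definitely attributable to the investigational drug must be reported".

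Other sections use wider terms. Under Definitions, an event is related if "more likely than not it was caused by the research activity". Sponsor Reporting says: "The Sponsor will be promptly notified of all SAEs that are related to the study intervention and unanticipated/unexpected". The IRB's 10-day rule and the rule on deaths both speak of a relation to the research.

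The drain belongs to the randomized package. Footnote 1 of the Calendar of Procedures and Assessments reads "Silo placement only or silo and JP drain placement per randomized group assignment", and the DPR Group section places the drain inside the abdomen. Risks and Benefits says that "the risk for infection secondary to placement and retention of the JP drain, for the DPR group, is unknown". Drain manipulation says: "There will be no increased risk of underlying infection with placement of the silo or drain".

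**The concern.** The experimental arm differs from standard care by more than a drug. The Investigational Product section describes Dianeal only, but each DPR infant also has a drain in the abdomen until closure, and infants in both arms give research blood samples. An assessor who answers step 1 exactly as worded can grade a drain injury, or harm from the research draws, as Unrelated. The same event would be related under the protocol's own definition.

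Two things are at stake: the causality code on the event, and whether the report is made promptly or waits for periodic reporting. This matters because safety is one of the two primary objectives, the arm is small, and the drain is a component whose infection risk the protocol itself calls unknown.

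**Working it through.** No arithmetic applies, because the plan gives no figure that bears on this point. The check is to list each object of causality and ask what it covers. The last three columns are my reading of the ordinary meaning.

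| Place in the protocol | Object of causality | Dianeal | JP drain | Research blood draws |
|---|---|---|---|---|
| Steps, step 1 | investigational drug | yes | no | no |
| Steps, step 2, first sentence | the agent | yes | no | no |
| Steps, note on events after 30 days | investigational drug | yes | no | no |
| Monitoring, Recording and Reporting of AEs, characteristics that determine reporting | study treatment | yes | arguable | doubtful |
| Sponsor Reporting, SAEs | study intervention | yes | yes | arguable |
| Institutional Review Board Reporting | the research | yes | yes | yes |
| Sponsor Reporting, deaths | research | yes | yes | yes |
| Definitions, Related | research activity | yes | yes | yes |
| Monitoring, Recording and Reporting of AEs, SAEs after the study period | study treatment or participation | yes | yes | yes |

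Three of the nine places are confined to the drug, and all three lie in the attribution steps. Those steps are narrower than the definition of related and narrower than each expedited route they feed.

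Three cases show the effect of a literal reading:

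1. *A DPR infant on Dianeal has an injury caused by the drain.* Step 1 gives Unrelated. The definition gives related, and the relatedness test of the IRB and sponsor routes is met.
2. *A DPR infant has the drain but no Dianeal yet.* The note closing the Eligibility Criteria allows randomization and silo placement by arm before all laboratory results are in, with values verified before DPR starts. An event in that interval cannot be related to the drug, although it can be caused by the drain.
3. *A standard-care infant is harmed by research sampling.* Research Laboratory Tests gives this arm a research lactate every 24 hours, and research sampling may take up to 2 mL per day. The infant never receives the drug, so step 1 has no meaningful answer.

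The possible delay can be read from the reporting rules. A qualifying unanticipated problem goes to the IRB within 10 days; other adverse events wait for continuing review, which the protocol describes as annual. A related and unexpected SAE goes promptly to the sponsor; other SAEs go to the sponsor and FDA in the Annual Progress Report.

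Separately, Drain manipulation asserts that there is no added infection risk, while Risks and Benefits calls the drain's infection risk unknown and then estimates that it is not appreciably higher than with standard repair. The first statement cannot stand beside the second.

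**The case against.** The strongest reply is that step 1 does not decide anything alone. It lists categories, sets no threshold, and does not say that a grade of Unrelated ends the assessment. The operative criteria follow directly below it and are wider, so a careful assessor would still expedite an unexpected drain injury. An assessor could also count drain harm as related because Dianeal is given through the drain and catheter infections and complications are among the listed possible reactions. This stands, and it limits the point. It does not remove the conflict, since no passage says which wording governs and the only graded scale carries the narrow one.

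A reader might infer that drain harm drops out of the record, or that the trial could report no related serious events while the package caused some. The documents do not support that. All adverse events in the study period must be recorded, and those not expedited still go to continuing review or the annual report. Data Analysis plans no table of related events. Much drain harm is also captured whatever its cause. Drain or catheter infections are collected data, infections are events of special interest, and bloodstream infection and intestinal perforation are serious by the adverse event table. A positive blood culture or documented peritonitis ends study drug.

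Expectedness also weakens the consequence. Infection, organ injury, peritonitis and catheter complications are listed in the protocol, so many drain events would count as expected, and would not be expedited, even with a wide relatedness question. Events more severe than listed would remain.

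A reader might also apply the 12.5% in Risks and Benefits to the DPR arm as a measure of drain harm. It is the infection risk of standard repair, hence background in both arms. The documents give no rate of drain-caused events.

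**Conclusion.** The attribution steps conflict with the protocol's own definition of related and with its IRB, sponsor and death criteria. The effect is limited to a possible wrong causality code and a possible delay from expedited to periodic reporting. By design it could touch the drain in the 20 planned DPR infants and research sampling in all 40 subjects. How many events would be affected cannot be estimated from the documents.

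This rests on two assumptions. The first is that some assessors will answer step 1 literally and treat the drain as distinct from the investigational product. The second is that the duty to record all adverse events covers the time between drain placement and the first dose. The Study Period paragraph starts recording at study drug, which should be read together with that duty.

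The reason given for removing a subject under Subject Withdrawal also names the investigational product. That list is permissive and includes the subject's best interest, so no change there is needed for this point. The correction is worth making because safety is a primary objective and the cost is very small.

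**What to change.** In step 1, step 2 and the note on events more than 30 days after the last dose, use one causality object that matches the definition of related: the study intervention (Dianeal, the JP drain and its handling) or another research procedure, such as research blood draws. Preferably, let the AE form record whether attribution is to dialysate, drain or other research procedure, and count an event as related if any one of these qualifies. Reconcile the infection-risk sentence in Drain manipulation with Risks and Benefits.

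The cost is a wording amendment and, if adopted, extra boxes on one form. The downside is that a few more events may be classed as related and expedited.
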